Objectives:	
Optimize the low cost FNS by comparing to SOC scopes at Duke University Medical Center
 
We will compare the use and reliability of the FNS scope to SOC scopes available at Duke University Medical Center. This will include image quality to see structures, lighting, and steering mechanism. Key objectives include ease of use, image quality, and perceived pain. The technical and subjective feedback will optimize the device to gain efficiencies and improve tolerability. Success is considered to be that the FNS is overall non-inferior to the current SOC scopes.
 
The expected outcome is to have an optimized FNS scope for production and widespread implementation and use

Population:	Up to 50 subjects 18 years or older who meet clinical criteria to undergo a SOC endoscopic exam
Phase or Stage:	N/A
Number of Sites:	1 site
Description of Intervention:	The FNS is used for assessment of the entire upper aerodigestive tract by Ear, Nose, and Throat (ENT) doctors or otolaryngologists and is part of SOC in the USA. This scope is inserted through the nasal passages into the pharynx, enabling a full view of all areas at risk for Head and Neck Cancer (HNC). Study participation ends once the post intervention survey is completed.
Study Duration:	3 months
Subject Participation Duration:	About 30 minutes
Estimated Time to Complete Enrollment:	2 months

Recruitment: Adult subjects that will undergo SOC endoscopy at the Head and Neck Surgery and Communication Sciences clinic at Duke will be approached by their treating physician if they would be interested in participating in this study. If they are interested, the study team will approach them to review the written consent form. Once signed, the SOC procedure will take place followed by the study scope procedure. The physician will complete their portion of the post procedure survey and assess for adverse effects. The subject will complete a single question on the survey focused on comparing the pain from both procedures.

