3.1 Primary

Objective	Brief Description/Justification of Outcome Measure	Outcome Measured By	Time Frame
Assess ease of use by end users between the SOC scope and FNS	We are comparing the ease of use between the FNS to the SOC scope. This will impact the design considerations and modification for the prototype optimization.	Compared with the first scope, how easy was the second scope to use? Very Hard 1 Harder 2 Same 3 Easier 4 Very Easy 5	Up to 2 months

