12.3 Final Analysis Plan

Statistical Analysis – Aim 1: Optimization Phase.

1. Outcome 1 (Primary): The primary outcome is ease of use comparison between the FNS to the SOC scope (score of 1 – 5, with 1 being very hard and 5 being very easy).
2. Outcome 2 (Secondary): Quality of the image (image quality score range 1-5, with 1 being poor and 5 being excellent).
3. Outcome 3 (Secondary): Perceived pain between the FNS to the SOC scope (pain score range of 1 – 3, with 1 being much more and 3 being much less).

Scenario 1:

Success of this first phase 1 (Aim 1) after evaluating 37 subjects is defined as - (1) at least 90% response of ease of use of second scope compared to first score to range from same to excellent (3 to 5); and (2) 90% responding to better video quality of second scope compared to first (score ranging from same to excellent (3 to 5); and (3) 90% responding to pain score of same or much less (2 or 3); In short, this phase is a success if 90% respond to same to excellent/much less on all 3 of the outcomes.

[figure not shown]
Scenario 2: If the rate is between 50 to < 90% for any three outcomes in a sample from 37, then the plan is to proceed recruiting more subjects until 50 are recruited. At 50 subjects, if in scenario 1 then phase 1 is a success and phase 1 is complete; if not, fine tune the prototype.

Scenario 3: If the rate is < 50% for any one of the 3 outcomes described above, then the plan is to proceed to fine tuning the prototype.

The primary outcome of ease of use of scope as reported by the physicians, will be examined between the two different scopes, at the simplest level, using paired Z-test if the scores (or transformed scores) are normally distributed or by using Wilcoxon test if the scores are non-normal.

The analysis for secondary outcomes of the change in the quality of the videos and pain will each be examined using paired Z-test, if the change (or transformed scores) is normally distributed or by Wilcoxon test if the change is non-normal. Assumptions of each of these tests will be examined. The significance of each of the outcomes will be examined at alpha = 0.05. The reliability of this instrument (using intra-class-correlation (ICC)) will be first assessed by using the data from the first 50 subjects. If ICC is < 0.9, we will include training component and necessary adjustment for the physicians.

See diagram below

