Piker, E. G., Schulz, K., Parham, K., Vambutas, A., Witsell, D., Tucci, D., Lee, W. T. (2016). Variation in the Use of Vestibular Diagnostic Testing for Patients Presenting to Otolaryngology Clinics with Dizziness. *Otolaryngol Head Neck Surg*, 155(1), 42-47. doi:10.1177/0194599816650173

Powell, B. J., McMillen, J. C., Proctor, E. K., Carpenter, C. R., Griffey, R. T., Bunger, A. C., Glass, J. E., York, J. L. (2012). A compilation of strategies for implementing clinical innovations in health and mental health. *Med Care Res Rev*, 69(2), 123-57. doi: 10.1177/1077558711430690.

Powell, B. J., Waltz, T. J., Chinman, M. J., Damschroder, L. J., Smith J. L., Matthieu M. M., Proctor, E. K., Kirchner, J. E. (2015). A refined compilation of implementation strategies: results from the Expert Recommendations for Implementing Change (ERIC) project. *Implement Sci*, 12, 10:21. doi: 10.1186/s13012-015-0209-1.

Schroy, P. C., 3rd, Wilson, S., & Afdhal, N. (1996). Feasibility of high-volume screening sigmoidoscopy using a flexible fiberoptic endoscope and a disposable sheath system. *Am J Gastroenterol*, 91(7), 1331-1337.

Vo, Q. T., Pham, D., Choi, K. J., Nguyen, U. T., Le, L., Shanewise, T., Lee, W. T. (2017). Solar-powered hearing aids for children with impaired hearing in Vietnam: a pilot study. *Paediatr Int Child Health*, 1-6. doi:10.1080/20469047.2016.1276119

SUPPLEMENTAL MATERIALS

Post-Procedural Survey By Clinician who performed the scope exam

(Provider questions once the SOC and study FNS exams are completed):

TECHNICAL ASSESSMENT OF FNS

Were you able to complete the first scope procedure to your satisfaction?

1=no 2=somewhat 3=yes

Were you able to complete the second scope procedure to your satisfaction

1=no 2=somewhat 3=yes

Were you able to view all the structures of concern using first scope ? Y/N

If no, please explain:

Were you able to view all the structures of concern using second scope ? Y/N

If no, please explain:

Did the patient appear to have more, the same, or less discomfort with the second scope?

much more about the same much less
1 2 3

If much more: please describe why:

Were there technical issues with the second prototype scope? Y/N (if Yes, please explain below)

- _____ steering
 - _____ lighting
 - _____ video
 - _____ fogging
 - _____ image capture
 - _____ other

Ease of use: Aim 1:

Compared with the first scope, how easy was the second scope to use?

Very hard Harder same Easier Very easy

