If harder or very hard: please explain:

Quality of Images: Aim 1

Rate the video quality of the first scope: (Poor) 1 2 3 4 5 (Excellent)

Rate the video quality of the second scope: (Poor) 1 2 3 4 5 (Excellent)

Did the subject experience an AE: Y / N

If yes - please provide additional information below:

Name of adverse event: _____

Brief description of the problem or event:

Severity of adverse event (using scale below):

1. Mild: no intervention required
2. Moderate: minimal, local, or non-invasive intervention indicated
3. Severe: significant symptoms requiring invasive intervention; subject seeks medical attention

Is the adverse event related to study procedure?

1. **If related**, please specify: Possibly, Probably, or Definitely related
 - a) The event is known to occur with the study intervention, and/or
 - b) There is a temporal relationship between the intervention and event onset and/or
 - c) The event abates when the intervention is discontinued, and/or
 - d) The event reappears upon a re-challenge with the intervention.
2. **If not related**, please specify if unlikely related or Not Related)
 - a) There is no temporal relationship between the intervention and event onset, and/or
 - b) An alternate etiology has been established.

Is the problem/event unexpected? Y/N

Does the event meet the definition of a serious adverse event? Y/N

If yes, check criteria below:

A serious adverse event (SAE) is one that meets one or more of the following criteria:

1. Results in death

-
- 2. Is life-threatening (places the subject at immediate risk of death from the event as it occurred)
 - 3. Results in inpatient hospitalization or prolongation of existing hospitalization
 - 4. Results in a persistent or significant disability or incapacity

An important medical event that may not result in death, be life threatening, or require hospitalization may be considered an SAE when, based upon appropriate medical judgment, the event may jeopardize the subject and may require medical or surgical intervention to prevent one of the outcomes listed in this definition.

Outcome of adverse event: resolved or unresolved

Date of resolution:

For enrolled subjects

Pain Comparison: Aim 1-secondary objective

Did you experience more, the same, or less pain/discomfort with the second scope compared with the first scope?

much more about the same much less

1 2 3

CONSENT FORM FOR PARTICIPATING IN RESEARCH

Duke's IRB approved consent form will be provided separately

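### The paired between-scope test planned for ease of use (primary) and pain does not fit items that give one comparative score per subject; Section 12.3 should state a one-sample analysis with a reference value.

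*Combined protocol and SAP*

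**What the plan says.** **Planned tests (Section 12.3).** For the primary outcome: "The primary outcome of ease of use of scope as reported by the physicians, will be examined between the two different scopes". The method is a paired Z-test if the scores are normal, otherwise a Wilcoxon test. For the other two outcomes: "The analysis for secondary outcomes of the change in the quality of the videos and pain will each be examined using paired Z-test", again with Wilcoxon as the fallback. Each outcome is tested at 0.05. No null value is given and sidedness is not stated.

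**What is collected.**
- *Ease of use* (Sections 3 and 3.1, and the clinician survey in the Supplemental Materials): one question, "Compared with the first scope, how easy was the second scope to use", scored 1 to 5 with 3 as same.
- *Pain* (Sections 3 and 3.2, and the subject survey): one question, "Did you experience more, the same, or less pain/discomfort with the second scope compared with the first scope", scored 1 to 3 with 2 as about the same. The Protocol Summary confirms this under Recruitment: "The subject will complete a single question on the survey focused on comparing the pain from both procedures".
- *Video quality* (the same survey): two ratings, one per scope. The first is "Rate the video quality of the first scope: (Poor) 1 2 3 4 5 (Excellent", followed by the matching item for the second scope.

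**Aim and decision rule.** Sections 4 and 12.1 set non-inferiority to the SOC scope as the goal. Scenarios 1 to 3 in Section 12.3 decide success, further recruitment or redesign from the percentage scoring 3 to 5 on ease and 2 or 3 on pain, with video judged alongside. Section 12.2 sizes the study on a confidence interval for a proportion.

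**The concern.** A paired test takes two scores per subject, one under each condition, and analyses their difference. For ease and pain the comparison is already inside the single score, so no SOC value exists to subtract. Section 12.3 describes ease as a score from very hard to very easy compared between two scopes. That wording suits a separate rating per scope, which the survey does not collect.

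Two things follow. First, whoever analyses the primary outcome must choose a different test and a null value, possibly after seeing the data, because the plan supplies neither. Second, the obvious substitute, testing the comparative score against same, is a test for a difference. A non-significant result from it does not show that the new scope is non-inferior.

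**Working it through.** **1. Scores available against scores needed.** A paired test needs one SOC score and one FNS score per subject.

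| Outcome | Scores per subject | SOC score to pair | Paired test possible as written |
|---|---|---|---|
| Ease of use (primary) | 1, comparative | 0 | No |
| Pain | 1, comparative | 0 | No |
| Video quality | 2, one per scope | 1 | Yes |

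The clinician's own discomfort item, "Did the patient appear to have more, the same, or less discomfort with the second scope", is also comparative, so it does not supply an SOC pain score.

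**2. The plan's own figure.** Section 12.2 gives n = 37 for a two-sided 95% interval of width 0.2 at a proportion of 0.9, with limits 0.76 and 0.96. The Wilson interval has
- centre = (p + z²/2n) / (1 + z²/n)
- half-width = z·√[p(1−p)/n + z²/4n²] / (1 + z²/n)

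With p = 0.9, z = 1.96 and n = 37, the centre is 0.8624 and the half-width 0.0994. The limits are 0.763 and 0.962 and the width is 0.199. At n = 36 the width is 0.2016, so 37 is the smallest n that meets the target. The figure reproduces. It concerns a proportion only and does not involve the paired test.

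**3. Does the unstated choice of test matter?** The counts here are assumed for illustration and are not in the documents: 37 subjects with ease scored 10 harder (2), 24 same (3) and 3 easier (4). Let d = score − 3.

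- *Proportion at 3 or above:* 27/37 = 0.730, Wilson 95% interval 0.570 to 0.846. This misses the 90% rule.
- *One-sample Z:* mean d = (3 − 10)/37 = −0.189. Variance = (13 − 49/37)/36 = 0.324, so SD = 0.569 and SE = 0.569/√37 = 0.0936. Z = −2.02, p = 0.043.
- *Signed-rank, normal approximation without continuity correction:* all 13 non-zero values have size 1, so z = (3 − 10)/√13 = −1.94, p = 0.052.
- *Exact sign test:* 2 × P(X ≤ 3 | 13, ½) = 2 × (1 + 13 + 78 + 286)/8192 = 0.092.

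The same data fall on both sides of 0.05.

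**4. Difference test against the stated aim.** Take a second assumed set with 8 harder, 26 same and 3 easier. The proportion at 3 or above is 29/37 = 0.784, again short of 90%. The three p-values are 0.125 (Z), 0.132 (signed-rank) and 0.227 (sign). All three tests read as not significant while the device fails the plan's own criterion.

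**The case against.** The strongest reply is that a paired Z-test and a Wilcoxon signed-rank test both reduce to one within-subject difference tested against no difference. A comparative item supplies such a contrast directly. Section 3.1 describes the outcome as a comparison ("We are comparing the ease of use between the FNS to the SOC scope"), and for pain the word change in Section 12.3 leans the same way. On that reading only the reference value is missing.

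Part of this stands. The data can be analysed with a one-sample test against 3 for ease and 2 for pain. But the plan does not say that the comparative score is to be treated as a difference, and it gives no reference value. For ease it speaks of scores compared between two scopes. The one-sample reading has to be supplied by the analyst.

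A reader might also infer that the primary outcome is left with no workable analysis, or that the go/no-go decision is blocked. The documents do not support that. Scenarios 1 to 3 apply the 50% and 90% thresholds to the comparative ease and pain scores as collected, and Section 12.2 already gives a confidence interval for that kind of proportion. Nor does the plan anywhere say that a non-significant test would be taken as non-inferiority. That is a risk to close off, not an error already made.

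**Conclusion.** The stated test does not match the data for two of three outcomes, including the primary, and it needs replacing. It rests on the survey items as printed and needs no assumption about results. The p-values in the illustration do depend on assumed counts. They show only that an unspecified test can change the reading (0.043 to 0.092 on one data set), not that it will.

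The consequence is limited. The success rule, the extension to 50 subjects and the basis for 37 are unaffected, and the collected data remain analysable. This is a should-fix correction to the analysis text. It does not invalidate the study.

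**What to change.** In Section 12.3:

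1. For ease of use and pain, replace the paired test with the proportion at same or better (ease 3 to 5, pain 2 or 3) and its 95% confidence interval. Name the interval method; Wilson reproduces the limits in Section 12.2. This matches both the sizing and Scenario 1.
2. If a hypothesis test is kept for these two outcomes, prespecify a single one-sample test, for example the signed-rank test, against the neutral category (3 for ease, 2 for pain). State its sidedness, and state that a non-significant result is not evidence of non-inferiority.
3. Keep the paired test for video quality only.

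The cost is a few sentences of protocol wording, with no change to the survey, the sample size or the decision rule.

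The alternative is to rate ease and pain separately for each scope, so that a true pair exists. It costs more than the extra survey lines. If those ratings replaced the comparative items, scores of 3 and 2 would no longer mean same, and the Scenario 1 cut-offs would have to be redefined. It would also have to be settled before enrolment, because participation ends once the survey is completed and a missing SOC rating could not be recovered under the plan.

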This technical and subjective feedback from subjects and providers will be used to optimize the device during the Optimization Phase. Each outcome measure as described in Section 3.1 and 3.2 will be compared between the SOC scope to the low cost FNS and used as a basis for modifications. For example, if the low-cost FNS image quality is noted to have lower ratings compared to the SOC scope due to inadequate lighting, modifications will be made to increase the light output for the next prototype.

The goal is to modify the prototype so that the outcome measures from the low cost FNS meet or exceed the outcome measures from the SOC scope. If this is the case, no

further prototypes will need to be performed for the optimization phase. Thus, the threshold for success will be noninferiority of the FNS compared to the SOC scope.

In addition to survey feedback, the FNS will have capacity to capture anonymized images of the upper aerodigestive tract such as the oropharynx, larynx, and nasopharynx. These will be collected and stored to a centralized image library. There will be no link to the subject, thus preventing loss of confidentiality.

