12 STATISTICAL CONSIDERATIONS

12.1 Study Hypotheses

The study hypothesis is that a low cost FNS can be non-inferior to the SOC scope in terms of ease of use, image quality, and perceived pain.

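### Non-inferiority is the stated claim, but no margin is given and the planned tests look only for a difference, so finding the two scopes similar would not establish it

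*Combined protocol and SAP*

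**What the plan says.** Non-inferiority appears in three places. The Protocol Summary, under Objectives, says: "Success is considered to be that the FNS is overall non-inferior to the current SOC scopes". Section 4 says: "Thus, the threshold for success will be noninferiority of the FNS compared to the SOC scope". Section 12.1 makes it the hypothesis for ease of use, image quality and perceived pain: "The study hypothesis is that a low cost FNS can be non-inferior to the SOC scope". None of them gives a margin, and no other section does.

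Section 12.3 then does two separate things.

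- **A decision rule on observed rates.** After 37 subjects, "this phase is a success if 90% respond to same to excellent/much less on all 3 of the outcomes". A rate from 50% to below 90% leads to recruitment up to 50, where the same rule is applied again. A rate below 50% on any outcome leads to changes to the prototype.
- **Tests.** The primary outcome is compared between scopes "using paired Z-test if the scores (or transformed scores) are normally distributed or by using Wilcoxon test if the scores are non-normal". The secondary outcomes are handled in the same way, and "The significance of each of the outcomes will be examined at alpha = 0.05". No shifted null, confidence bound or sidedness is given, and nothing links a test result to the 90% rule.

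Section 12.2 sizes the study on the width of a confidence interval for one proportion. It also gives a second version of the success rule: an observed proportion between 0.76 and 0.96 at 37 subjects.

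**The concern.** A non-inferiority claim needs a stated largest acceptable deficit and an analysis that rules out anything worse. A paired Z or Wilcoxon test judged for significance has, by default, a null of no difference. Failing to reject that null may mean that the scopes are alike, or only that the sample is small or the ratings scattered. The usual Wilcoxon signed-rank test also drops zero differences, so every rating of 'same', which the success rule counts as favourable, leaves that test.

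At stake is the statement the study can make at the end. Section 4 ties the end of prototype work to non-inferiority, and the Protocol Summary says the data inform the final adjustments before the Vietnam phase. A report that quotes a non-significant p-value as support for the 12.1 hypothesis would follow the plan as written and still be unsupported.

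**Working it through.** **The plan's own figure.** The Wilson score interval at p = 0.9, n = 37, z = 1.96:
- centre = (0.9 + 3.842/74) / (1 + 3.842/37) = 0.862
- half-width = 1.96 × √(0.09/37 + 3.842/(4 × 37²)) / (1 + 3.842/37) = 0.099
- limits 0.763 and 0.962, width 0.199

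This reproduces the 37 subjects, the width of 0.2 and the limits 0.76 and 0.96 in 12.2. It is a precision calculation. The 80% power quoted beside it plays no part, and no non-inferiority test was sized.

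**Set-up for the test examples.** Ease of use is a single comparative item with 3 meaning same, so I take d = score − 3 and test its mean against 0. With x ratings one step better and y one step worse out of n:
- mean = (x − y)/n
- s² = [(x + y) − (x − y)²/n]/(n − 1)
- Z = mean/(s/√n)
- same-or-better rate = (n − y)/n

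The data sets are constructed, two-sided p-values are assumed, and 'exact Wilcoxon' is computed on the non-zero differences.

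**1. Non-significance without similarity.** n = 37, 13 same, 12 easier, 12 harder.
- mean = 0, s² = 24/36, s = 0.816, standard error 0.134
- Z = 0, p = 1.0; 95% CI −0.26 to 0.26
- same or better = 25/37 = 67.6%

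**2. Test favours the FNS, rule not met.** n = 50, 44 easier, 6 harder.
- mean = 38/50 = 0.76, s² = (50 − 38²/50)/49 = 0.431, standard error 0.093
- Z = 8.19; exact Wilcoxon p < 0.0001
- same or better = 44/50 = 88%, so 12.3 calls for changes to the prototype

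At n = 37, 33 easier and 4 harder is 89.2% with Z = 7.57, and 12.3 extends recruitment.

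**3. The 0.76 to 0.96 rule met, test against the FNS.** n = 37, 29 same, 8 harder.
- same or better = 29/37 = 78.4%, a success under 12.2 (under the 90% rule of 12.3 it is not)
- mean = −8/37 = −0.216, s² = (8 − 64/37)/36 = 0.174, Z = −3.15, p = 0.002
- exact Wilcoxon on 8 non-zero values: p = 2 × 0.5⁸ = 0.008

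**4. Power of the planned test to see a deficit.** Power = Φ(k√n − 1.96) for a true deficit of k SD. At k = 0.3 it is 45% at n = 37 and 56% at n = 50. In points the answer depends on the SD. A 0.3-point deficit at n = 37 is missed in about 5%, 32%, 55% or 69% of cohorts at SD 0.5, 0.75, 1.0 or 1.25. Whether 0.3 points counts as inferior cannot be said without a margin.

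**5. Margin that the planned sample can support.** On the mean scale, with one-sided 0.025, 80% power and no true difference, margin = SD × (1.960 + 0.842)/√n.

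| Assumed SD | n = 37 | n = 50 |
|---|---|---|
| 0.5 | 0.23 | 0.20 |
| 0.75 | 0.35 | 0.30 |
| 1.0 | 0.46 | 0.40 |

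On the same-or-better scale, the exact 95% lower limit must exceed a floor p0. Power is at a true rate of 0.90.

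| Floor p0 | Needed of 37 | Power | Needed of 50 | Power |
|---|---|---|---|---|
| 0.70 | 32 | 84% | 42 | 94% |
| 0.75 | 34 | 49% | 44 | 77% |
| 0.80 | 35 | 27% | 46 | 43% |

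For comparison, the 90% rule itself needs 34 of 37 (0.9 × 37 = 33.3) and 45 of 50. These floors and SDs are illustrations, not proposals.

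**The case against.** The strongest reply is that nothing depends on the tests. Section 12.3 defines success and every next step by the same-or-better rate, section 12.2.2 calls this an optimization study, and section 4 describes the goal as FNS measures at least as good as those of the SOC scope. On that view the 90% rule is the working definition of non-inferiority and the tests are supplementary.

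Much of this stands. A reader might infer that the plan leaves the go/no-go decision open between a rule and a p-value. It does not: the rule decides. A reader might also infer that the tests can never support the claim. That is too strong, because a significant result in favour of the FNS would imply non-inferiority at any margin.

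A third tempting reading is that a cohort can pass the 90% rule and be significantly worse on the same data. The example is 45 same and 5 harder of 50: exactly 90%, Z = −2.33, p = 0.020, large-sample Wilcoxon p = 0.025. But 12.3 allows the Z-test only for normal scores, which these are not, and the exact Wilcoxon p is 2 × 0.5⁵ = 0.0625. At 37 subjects the corresponding passing case, 34 same and 3 harder, gives Z-test p = 0.075 and exact Wilcoxon p = 0.25. That conflict is not established for ease or pain under the 90% rule at 37.

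What the reply does not answer is that the 90% rule is an observed proportion with no confidence bound, that nothing calls it (or the 0.76 limit in 12.2) a margin, and that the only inference planned for the 12.1 hypothesis addresses a different question. The diagram in 12.3 is not shown in the text available, so I cannot exclude that it says more about the tests.

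**Conclusion.** The concern holds for the inferential conclusion, not for the prototype decision. Non-inferiority is claimed, no margin is stated, and the planned tests, on their ordinary reading, have a null of no difference. The result to be expected from two similar scopes would therefore support nothing: p = 1.0 is compatible with one subject in three rating the FNS harder (12 of 37). The tests have no stated role. They can disagree with the 90% rule in the FNS's favour (88% with Z = 8.19) and with the 12.2 version of the rule against it (78.4% with exact p = 0.008).

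This rests on two readings of the text: that the unstated null is no difference, and that single comparative items are tested against their midpoint. The absence of a margin depends on neither. Every figure that needs an SD is an assumption, because the documents give none. The point should be settled before the first subject, since a margin chosen after the ratings are seen would carry little weight.

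**What to change.** In 12.3, for each outcome:

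1. State a margin before the first subject. It can be a minimum acceptable same-or-better proportion, which stays on the scale of the existing success rule. For video this would mean an FNS rating at least equal to the SOC rating in the same subject. Or it can be a mean difference (video: FNS minus SOC; ease: score minus 3; pain: score minus 2).
2. Report the estimate with a two-sided 95% confidence interval, and conclude non-inferiority only if the lower limit lies above the margin. This replaces the difference tests as the basis for that conclusion.
3. State that the 90% rule governs the prototype decision and the interval governs the non-inferiority claim. This is needed because the two can part. On the mean scale, 26 same and 11 one step worse of 37 has mean −0.30 and lower limit −0.45, which clears an illustrative 0.5-point margin, yet only 70% are same or better.
4. Label any difference-test p-values descriptive.

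The cost is wording and three margins; no new data items are needed. The downside is that the claim becomes harder to meet, and 37 to 50 subjects limit the margin that can be supported. At an assumed SD of 1.0, with 80% power and no true difference, a 0.5-point margin needs 32 subjects but a 0.25-point margin needs 126. If the sponsor wants a tighter margin than the sample can support, the alternative is to drop the word non-inferiority and report the estimates with their intervals.
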